5. AMENDMENTS AND UPDATES

Amendment number	Date	Protocol section(s) changed	Summary of amendment(s)	Reason
Version 3.0	13 February 2023	Section: STUDY INFORMATION	
Change of protocol version identifier from "version 2.0" to "version 3.0" and the date from "12 November 2021" to "13 February 2023"
 
Change of "Secondary objective" with the deletion of "To evaluate efficacy of current treatment for Canadian breast cancer patients using surrogates for time to next treatment in the real-world setting including:
 
• The length of treatment for the first line (TTNT1), the length of treatment for the second line (TTNT2), the time from cyclin-dependent kinase 4 and 6 (CDK4/6) inhibitor to starting chemotherapy (TTC) and overall survival (OS)• The length of treatment for short term versus long term responders" 
which is now included with the exact similar wording to the CCI [REDACTED] section, except for the following wording "...the time from cyclin-dependent kinase 4 and 6 (CDK4/6) inhibitor to starting chemotherapy (TTC)..." which was replaced by "...the time from the date of ABC/MBC diagnosis to starting chemotherapy (TTC)..."
 
Change of "The authors" section, the author and contact information of PPD [REDACTED], PhD Director of Clinical Operations and Head Scientist, PPD [REDACTED] PPD [REDACTED] is replaced by PPD [REDACTED], MPH, Clinical Program Lead, PPD [REDACTED]
	
The changes in the study information section are driven by the study protocol amendment.
 
The secondary objective was adapted as the initial planned sample size (e.g. 180 patients) will be dramatically lower than expected (less than 30% of initial sample size); CCI [REDACTED]
 
As per clinical expert insight, The definition of TTC was clarified to the time from the date of ABC/MBC diagnosis to starting chemotherapy
 
Change of staff at Pentavere (vendor) occurred: PPD [REDACTED]

PFIZER CONFIDENTIAL

			This latter change also applies to the section 3. Responsible Parties	
Version 3.0	13 February 2023	Section: LIST OF ABBREVIATIONS	Changed the definition of TTC from "Time from date CDK4/6 treatment to starting chemotherapy" to "time from date of ABC/MBC to starting chemotherapy"	This change was requested by PPD [REDACTED] as this is a more appropriate way of deriving TTC

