9.3. Variables

Table 1. List of study variables to be extracted (where feasible)

Variable	Role	Data source(s)	Operational definition
Patient demographics	Baseline characteristic, potential confounder, sub-group identifier	Patient EHR	
• Date of birth• Sex• Date of death
Clinical characteristics	Baseline characteristic, potential confounder, sub-group identifier	Patient EHR	
• Date of ABC/MBC diagnosis• Age at ABC/MBC diagnosis (years)• ECOG performance score at index date (0, 1, 2, 3, 4)• ESAS• Date of last follow-up• Organ level metastatic sites (bone, brain, lungs, liver; number of sites)• Tumour stage at initial breast cancer diagnosis (I, II, III, IV, Unknown)• Tumour grade• Tumour histology• ER and PR receptor status (Positive, Negative, Unknown)• HER2 status (Positive, Negative, Unknown)• Concomitant LHRH agonists
Comorbidities	Baseline characteristic, potential confounder, sub-group identifier	Patient EHR	
• Atrial fibrillation• Hypertension• Coronary Artery Disease/Myocardial infarction/Angina• Diabetes Mellitus• Stroke
Treatments	Exposure	Patient EHR	
• Systemic Therapies (therapy start and stop date including combination therapies, and line of therapy)• Surgeries• Radiation Treatment
Clinical outcomes	Outcome	Patient EHR	
• TTNT1• TTNT2• TTC• Overall Survival (landmark 3y)

ECOG, Eastern Cooperative Oncology Group; EHR, Electronic Health Record; ER, Estrogen Receptor; ESAS, Edmonton Symptom Assessment System; HER2, Human Epidermal Receptor Growth Factor 2; LHRH, Luteinizing Hormone-Releasing Hormone; PR, Progesterone Receptor; TTC, time from date of ABC/MBC to starting chemotherapy; TTNT1, length of treatment for the first line; TTNT2, length of treatment for the second line

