4.4 SUBGROUPS

Subgroup analyses for the primary and secondary objectives will be conducted in patients who are potentially pre-menopausal, where possible. Patients who are 50 years old or younger and are on a LHRH antagonist will be included in this subgroup. Subgroup analyses will be descriptive in nature and will depend on adequate sample size.

The secondary objective will include the following subgroups for specified analyses, where possible:

[figure not shown]
- Pre-CDK subgroup is defined as ABC/MBC patients starting systemic therapy before the introduction of CDK 4/6 inhibitor (January 2016 to May 2016).
- Post-CDK subgroup is defined as ABC/MBC patients starting systemic therapy after the introduction of CDK 4/6 inhibitor (January 2019 to May 2019).

CCI

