5.5 ENDPOINTS

Variable	Role	Data source(s)	Operational definition
Patient demographics	Baseline characteristic, potential confounder, subgroup identifier	Patient EHR	
• Date of birth• Sex• Date of death
Clinical characteristics	Baseline characteristic, potential confounder, subgroup identifier	Patient EHR	
• Date of ABC/MBC diagnosis• Age at ABC/MBC diagnosis (years)• ECOG performance score at index date (0, 1, 2, 3, 4)• ESAS• Date of last follow-up• Organ level metastatic sites (bone, brain, lungs, liver; number of sites)• Tumour stage at initial breast cancer diagnosis (I, II, III, IV, Unknown)• Tumour grade

PFIZER CONFIDENTIAL

			
 • Tumour histology • ER and PR receptor status (Positive, Negative, Unknown) • HER2 status (Positive, Negative, Unknown) • Concomitant LHRH agonists
Comorbidities	Baseline characteristic, potential confounder, subgroup identifier	Patient EHR	
 • Atrial fibrillation • Hypertension • Coronary Artery Disease/Myocardial infarction/Angina • Diabetes Mellitus • Stroke
Treatments	Exposure	Patient EHR	
 • Systemic Therapies (therapy start and stop date including combination therapies, and line of therapy) • Surgeries • Radiation Treatment
Clinical outcomes	Outcome	Patient EHR	
 • TTNT1 • TTNT2 • TTC • Overall Survival (landmark 3y)

ECOG, Eastern Cooperative Oncology Group; EHR, Electronic Health Record; ER, Estrogen Receptor; ESAS, Edmonton Symptom Assessment System; HER2, Human Epidermal Receptor Growth Factor 2; LHRH, Luteinizing Hormone-Releasing Hormone; PR, Progesterone Receptor; TTC, time from date of ABC/MBC diagnosis to starting chemotherapy; TTNT1, length of treatment for the first line; TTNT2, length of treatment for the second line

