7.2 STATISTICAL ANALYSES

Treatment patterns and changes:

Treatment patterns among patients with HR+/HER2- ABC/MBC receiving Palbociclib will be analysed as the primary objective of this study. This analysis will be conducted in all patients who have received Palbociclib combination treatment. Subgroup analyses on patients who are likely to be pre-menopause might also be conducted if applicable. This analysis will be descriptive in nature and is subject to modification based on sample size and final data specifications. No statistical tests will be utilized. Continuous and categorical variables will be described using methods outlined in Section 7.1 of this document. Sankey diagrams and/or bar charts may also be used to illustrate sequencing and changes in treatment patterns if appropriate. The above-mentioned analyses will use the following or similar R packages: 'tables', 'ggplot', and 'networkD3'.

Type	Objective	Endpoint	Population	Statistical Method/Test	Covariates used	Method of adjustment for missing values	Role of the analysis related to study objectives
Table	1	Not applicable	- All patients who have received Palbociclib	Descriptive stats	Systemic therapies	Missing data will be summarized in table.	To describe treatment patterns during

PFIZER CONFIDENTIAL

			combination treatment. - Pre-menopausal patients ^a			Missing days from dates will be handled as per section 6 of this document.	study period.
Bar chart	1	Not applicable	- All patients who have received Palbociclib combination treatment. - Pre-menopausal patients ^a	Descriptive stats	Systemic therapies	Missing data will be excluded. Missing days from dates will be handled as per section 6 of this document.	To illustrate changes in treatment patterns by year.
Sankey diagram	1	Not applicable	- All patients who have received Palbociclib combination treatment. - Pre-menopausal patients ^a	Descriptive stats	Systemic therapies	Missing data will be excluded. Missing days from dates will be handled as per section 6 of this document.	To illustrate sequencing of treatments.

^a Patients who are potentially pre-menopausal may be analyzed as a subgroup for this objective. Please refer to section 4.4 of this document for further details about how this group is defined.

Pre- and Post-CDK treatment patterns:

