8 LIST OF TABLES AND TABLE SHELLS

PLEASE NOTE: The below tables and proposed analyses reflect the complete list of desired variables and analyses to be included in the study. However, inclusion of variables and type of analyses conducted will be dependent on availability of data from source documents and are subject to modification based on sample size and final data specifications.

Table 1: Demographics and Baseline characteristics of all patients and premenopausal patients.

Variables	Overall (N=) ^a	Premenopausal Patients (N=) ^b
Age		
N		
Mean (SD)		
Median		
Q1, Q3		
Minimum-Maximum		
Sex		
Female		
Male		
Unknown		
ECOG		
0		
1		
2		
3		
4		
Unknown		
Organ level metastatic site		
Bone		
Brain		
Lungs		
Liver		
Number of metastatic sites		
0		
1		
2		
3		
4		
Comorbidities		
Atrial fibrillation		
Hypertension		

PFIZER CONFIDENTIAL

Coronary Artery Disease/Myocardial infarction/Angina		
Diabetes Mellitus		
Stroke		
Tumour stage at diagnosis		
I		
II		
III		
IV		
Unknown		
Tumour grade		
1		
2		
3		
Unknown		
Tumour histology		
Lobular Carcinoma		
Ductal carcinoma		
Mixed		
DCIS		
LCIS		
Other		
Unknown		
ER Receptor status		
Positive		
Negative		
Unknown		
PR Receptor status		
Positive		
Negative		
Unknown		

^a Includes all study patients

^b Includes all study patients who are potentially in pre-menopause. Please refer to section 4.4 of this document for further details about how this group is defined.

Table 2: Demographics and Baseline characteristics of all Palbociclib treated patients and Palbociclib treated premenopausal patients.

Variables	Palbociclib treated patients (N=) ^a	Premenopausal Patients (N=) ^b
-----------	---	---

PFIZER CONFIDENTIAL

Age	N Mean (SD) Median Q1,Q3 Minimum-Maximum		
Sex	Female Male Unknown		
ECOG	0 1 2 3 4 Unknown		
Organ level metastatic site	Bone Brain Lungs Liver		
Number of metastatic sites	0 1 2 3 4		
Comorbidities	Atrial fibrillation Hypertension Coronary Artery Disease/Myocardial infarction/Angina Diabetes Mellitus Stroke		
Tumour stage at diagnosis	I II III IV Unknown		
Tumour grade	1		

PFIZER CONFIDENTIAL

2		
3		
Unknown		
Tumour histology		
Lobular Carcinoma		
Ductal carcinoma		
Mixed		
DCIS		
LCIS		
Other		
Unknown		
ER Receptor status		
Positive		
Negative		
Unknown		
PR Receptor status		
Positive		
Negative		
Unknown		

^a Includes patients who received Palbociclib treatment

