10 APPENDICES

10.1 APPENDIX 1: DATA DERIVATION DETAILS

Age at diagnosis: Age in years rounded down to nearest whole year

- Date of diagnosis – Date of birth)

Menopause status: Potential menopause status at diagnosis

- Patients ≤ 50 years old and on a LHRH antagonist may potentially be in pre-menopause.

A1.1 Definition and use of visit windows in reporting

A1.2 Further definition of endpoints

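### The potentially pre-menopausal subgroup is defined by LHRH antagonist use, but the only LHRH variable listed for extraction is LHRH agonists

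*SAP*

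**What the plan says.** **The rule.** SAP 4.4 plans subgroup analyses of potentially pre-menopausal patients and states: "Patients who are 50 years old or younger and are on a LHRH antagonist will be included in this subgroup". Appendix 1 of the SAP (10.1, data derivation details) gives the same rule under menopause status at diagnosis: "Patients ≤ 50 years old and on a LHRH antagonist may potentially be in pre-menopause".

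**The listed data.** Protocol Table 1 (section 9.3) and the variable table in SAP 5.5 each contain one LHRH item, under clinical characteristics: "Concomitant LHRH agonists". Neither table lists LHRH antagonists or menopausal status. The treatments row has a general entry, "Systemic Therapies (therapy start and stop date including combination therapies, and line of therapy", which names no LHRH drug.

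**Where the rule is used.** The footnotes to SAP Tables 1, 2, 6 and 10, and to the analysis tables in SAP 7.2 and 7.2.2, send the reader back to 4.4. The footnote to Table 1, for example, reads "Includes all study patients who are potentially in pre-menopause. Please refer to section 4.4 of this document". SAP 7.2 makes the analysis optional: "Subgroup analyses on patients who are likely to be pre-menopause might also be conducted if applicable".

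**The concern.** An LHRH agonist and an LHRH antagonist are different drug classes, and the rule asks for one while the variable lists supply the other. A programmer who follows 4.4 to the letter finds no listed LHRH variable to apply it to. A programmer who uses the LHRH variable that was extracted departs from the written definition. Both would put the same label on the column.

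The finished tables would not reveal which was done. The baseline shells (Tables 1 to 5) have no LHRH row, and the table footnotes only point back to 4.4.

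This is the only subgroup that SAP 7.2.2 lists for the treatment-pattern analysis under the primary objective. It is also the subgroup listed for treatment duration, time to chemotherapy and overall survival.

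**Working it through.** The plan gives no figure to reproduce for this subgroup: no expected size, no rate of LHRH use and no powered comparison. The check is therefore a comparison of texts, followed by a count of outputs and a ceiling on patient numbers.

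**1. Every operative LHRH mention**

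| Place | Function | Class named |
|---|---|---|
| SAP 4.4 | Subgroup definition | Antagonist |
| SAP 10.1, Appendix 1 | Derivation rule | Antagonist |
| Protocol 9.3, Table 1 | Variable list | Agonists |
| SAP 5.5 | Variable list | Agonists |

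The rule says antagonist in 2 of 2 places and the lists say agonists in 2 of 2. The remaining mentions only spell out the abbreviation. All four places are readable, so redaction does not explain the mismatch. Each wording is consistent within its own function, so counting occurrences does not show which word is the slip.

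**2. Who is classified differently (patients aged 50 or under)**

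| LHRH record | Rule as written | Rule on the listed variable |
|---|---|---|
| Agonist only | Out | In |
| Antagonist only | In | Out |
| Both | In | In |
| Neither | Out | Out |

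The two readings differ by exactly the patients aged 50 or under who received one class and not the other. The documents give no count for any row.

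**3. Outputs that show the subgroup (SAP section 8)**

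| Group | Outputs | Total | With subgroup |
|---|---|---|---|
| Baseline | Tables 1–5 | 5 | 2 (Tables 1, 2) |
| Primary objective | Table 6, Figures 1–4 | 5 | 3 (Table 6, Figures 3, 4) |
| Secondary objective | Tables 7, 8, Figure 5 | 3 | 0 |
| Time-to-event and responder | Figures 6–13, Tables 9, 10 | 10 | 5 (Table 10, Figures 10–13) |
| COVID-19 | Tables 11, 12, Figures 14–20 | 9 | 0 |
| **All** | 12 tables, 20 figures | **32** | **10** |

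10 / 32 = 31%. This shows how far the definition reaches. It does not measure a change in any result.

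**4. Ceiling on patients**

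The reason given for Protocol version 3.0 puts the expected cohort at "less than 30% of initial sample size", with 180 as the initial size: 0.30 × 180 = 54. The subgroup is a part of fewer than 54 patients. The number classified differently therefore lies between 0 and fewer than 54, and the documents do not narrow that range.

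**The case against.** The case for treating this as trivial has five parts.

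- **Consequence.** The subgroup is descriptive, is planned only where possible and with adequate numbers, and may never be reported. No hypothesis is tested and full-cohort results are untouched. This stands and limits how serious the point is. However, judging whether numbers are adequate needs a count of eligible patients, and that count depends on the disputed word.
- **It is an obvious slip.** The clinical characteristics row, which holds the agonist item, is labelled in part as a subgroup identifier, which suggests that agonists were meant. This is some evidence but not proof, because the demographics and comorbidities rows carry the same label. If it is a slip, it sits in both the definition and the derivation rule.
- **The subgroup may still be derivable.** An antagonist recorded as a systemic therapy could be found in the general treatment field. This is accepted, so the subgroup is not shown to be impossible to form. But no passage ties that field to the rule, and the lists give it the role of exposure.
- **Site extraction rules may settle it.** Protocol 9.8 has extraction rules developed with site clinicians, checked for concordance, and a dataset approved before lock. Those rules are not in the documents, so divergent programming is possible but not demonstrated. They govern how a variable is extracted, and the subgroup definition would still need correcting in the SAP.
- **Counting shells overstates the effect.** This is fair: 10 of 32 is reach, not bias.

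**Conclusion.** The concern holds. As written, the rule for the potentially pre-menopausal subgroup does not match the only LHRH variable listed for extraction, and applied literally it leaves out patients aged 50 or under recorded under that variable alone. The definition reaches 10 of 32 planned outputs, 3 of them among the 5 for the primary objective. No secondary-objective shell shows the subgroup, although SAP 4.4 plans it for that objective too.

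The number of patients affected is unknown. It is bounded only by the cohort ceiling of 54, which assumes that the shortfall stated in the protocol amendment applies to the final cohort. The documents do not establish which word was intended. The point should be fixed because it is an error in an operative derivation and is easy to correct. It does not threaten the study's main descriptive results.

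**What to change.** Before dataset lock, reconcile SAP 4.4 and Appendix 1 with Protocol Table 1 and SAP 5.5. The sponsor and site clinicians should confirm which class or classes are meant to identify potentially pre-menopausal patients. Then take one of two routes.

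- **(a) Define the subgroup on the listed variable:** age 50 or under at ABC/MBC diagnosis, and the concomitant LHRH agonist item recorded as yes. The age time point follows Appendix 1 and the listed variable for age at ABC/MBC diagnosis, but 4.4 does not state it and should. The same edit should say when LHRH use is assessed, since neither the rule nor the variable gives a time reference. *Cost:* a wording change in two SAP places.
- **(b) Add LHRH antagonists as a named item** to Protocol Table 1 and SAP 5.5, and use matching wording in all four places. *Cost:* one more extraction item with its own extraction rule. Because the protocol's variable list changes, a protocol amendment is also needed, and Protocol 10.3 requires prospective ethics approval of amendments. This is cheapest before data collection ends, planned for 31 March 2023.

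Under either route, the footnotes that point to 4.4 need no change.

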4. ABSTRACT

Title: Treatment Patterns and Clinical Outcomes Among Patients Receiving CDK4/6 inhibitors Combinations For HR+/HER2- Advanced/Metastatic Breast Cancer In A Canadian Real World Setting.

Version 3.0

Date of the abstract: 13 February 2023

Main Author and affiliation:

PPD

Rationale and background: Breast cancer is the main cause of cancer death in women worldwide, with hormone receptor positive (HR+) and human epidermal growth factor receptor 2 negative (HER2-) tumours being the most commonly diagnosed. Endocrine therapy is a mainstay of breast cancer treatment. In the PALOMA clinical trials, adding palbociclib resulted in greater median progression free survival (PFS) than endocrine therapy alone. Since its approval in Canada in 2016, palbociclib has been used in patients with HR+/HER2- advanced/metastatic breast cancer (ABC/MBC), but little is known about its real world use and clinical outcomes in a Canadian setting.

[figure not shown]
Research question and objectives: The primary objective of this study is to explore patient demographics, clinical characteristics, treatment patterns and changes, and clinical outcomes of adult female patients with HR+/HER2- ABC/MBC in Canada, who received a CDK4/6i based therapy for their ABC/MBC.

Study design, study size, and population: This study will be a retrospective chart review of patient records from Sinai Health based cancer clinics. All records from female patients ≥ 18 years old with HR+/HER2- ABC/MBC diagnosed at this site between 01 January 2016 and 01 July 2021 will be used. It is estimated that there will be approximately 300 diagnoses of ABC/MBC within the study period at Sinai Health, approximately 180 of which will be HR+/HER2-. Only patients who have taken a CDK4/6 inhibitor in combination with an endocrine therapy will be included in this study. Using electronic health records (EHRs) stored within Sinai Health, natural language processing (NLP) algorithms (ie, Pentavere's DARWEN™ technology) will be trained to extract data variables from the EHR data.

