9.2. Setting

The study period will extend from 01 January 2016 to 01 October 2021 (Figure 1). All female patients who are ≥ 18 years of age and are diagnosed with HR+/HER2- ABC/MBC and received a CDK4/6 inhibitor at Sinai Health during the study period will be included in the study. It is estimated that there will be approximately 300 diagnoses of ABC/MBC within the study period at Sinai Health, of which approximately 180 will be HR+/HER2-. Follow-up data from EHRs will be included up to the extent that they are available within the study period. Pre-index data (stage at initial breast cancer diagnosis, treatment being received at ABC/MBC diagnosis) may be extracted from EHRs up to 12 months before the index date.

[figure not shown]

Figure 1. Study Design Flow Chart

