4 ANALYSIS SETS/POPULATIONS

4.1 FULL ANALYSIS SET

Inclusion criteria

Patients must meet all of the following inclusion criteria to be eligible for inclusion in the study:

1. *≥ 18 year old female*
2. *HR+/HER2- breast cancer diagnosis with confirmed metastatic or advanced disease*
3. *Diagnosed with ABC/MBC between 01 January 2016 and 01 July 2021*
4. *Treatment with CDK4/6 inhibitor*

Exclusion criteria

Patients meeting any of the following will not be included in the study:

1. *Patient does not have ABC/MBC*
2. *Patient has indicated HR- or HER2+ status*
3. *Patient received a CDK4/6i as part of a clinical trial*

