4.3 OTHER ANALYSIS SET

The primary objective will include only patients who received at least one dose of Palbociclib during the study period.

The secondary and **CCI** objectives will include all patients in the full analysis set.

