Describing pre- and post-CDK treatment patterns and sequencing in ABC/MBC patients is one of the secondary objectives of this study. To explore treatment patterns and sequencing before the introduction of CDK4/6 inhibitor (“pre-CDK” subgroup), ABC/MBC patients diagnosed and starting systemic therapy before the introduction of Palbociclib in Canada (i.e. January 2016 to May 2016) will be investigated. To explore treatment patterns and sequencing after introduction of CDK4/6 inhibitors, a similar length of time (i.e. January – May) will be investigated; however, this will be done in 2019 to allow for sufficient time for education and uptake of CDK4/6 inhibitor usage in

PFIZER CONFIDENTIAL

[figure not shown]
clinical practice (“post-CDK” subgroup). The above dates are the time periods we propose based on clinical relevance, but they are contingent upon clinician input and review of primary objective results and are subject to change.

Treatment patterns for systemic therapy for the pre-CDK subgroup and post-CDK subgroup will be described. Sequencing of therapies received after CDK treatment will be described. Continuous and categorical variables will be described using methods outlined in Section 7.1 of this document. Bar charts may also be used to illustrate changes in treatment patterns over time if appropriate. The above-mentioned analyses will use the following or similar R packages: ‘tables’ and ‘ggplot’.

Type	Supports Protocol Objective Number	Endpoint	Population	Statistical Method/Test	Covariates used	Method of adjustment for missing values	Role of the analysis related to study objectives
Table	2	Not applicable	-Pre-CDK subgroup -Post-CDK subgroup	Descriptive stats Comparisons tests (e.g. t-test, ANOVA, Wilcoxon, Fischer)	Systemic therapies	Missing data will be summarized in table. Missing days from dates will be handled as per section 6 of this document.	To describe treatment patterns pre and post CDK.
Bar chart	2	Not applicable	-Pre-CDK subgroup -Post-CDK subgroup	Descriptive stats	Systemic therapies	Missing data will be excluded. Missing days from dates will be handled as per section 6 of this document.	To illustrate treatment patterns over time.

Time to event analysis:

PFIZER CONFIDENTIAL

CCI

Numbers

at risk and cumulative incidence will be reported for each curve. **CCI**

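### The 'pre-CDK' (January to May 2016) subgroup can hold only patients who later received a CDK4/6 inhibitor, so Tables 4 and 7 cannot describe general practice before introduction

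*SAP*

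**What the plan says.** **Who is in the study.** Criterion 4 in SAP 4.1, repeated in Protocol 9.2.1, is "Treatment with CDK4/6 inhibitor". The Protocol abstract says: "Only patients who have taken a CDK4/6 inhibitor in combination with an endocrine therapy will be included in this study". Protocol 9.2 takes women "diagnosed with HR+/HER2- ABC/MBC and received a CDK4/6 inhibitor at Sinai Health during the study period", a period that ends on 1 October 2021.

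**Which set the secondary objective uses.** SAP 4.3 says that the secondary and a further, redacted class of "objectives will include all patients in the full analysis set". The summary in SAP 7.2.2 agrees: it gives all patients as the analysis set and the pre- and post-CDK groups as its subgroups.

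**How the subgroups are described.** SAP 4.4 states: "Pre-CDK subgroup is defined as ABC/MBC patients starting systemic therapy before the introduction of CDK 4/6 inhibitor (January 2016 to May 2016"). The post-CDK group is the same definition moved to January to May 2019. SAP 7.2 gives the purpose of the first group as exploring treatment before introduction: "ABC/MBC patients diagnosed and starting systemic therapy before the introduction of Palbociclib in Canada (i.e. January 2016 to May 2016) will be investigated". The role of the table is "To describe treatment patterns pre and post CDK".

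**Outputs.** Table 4 (baseline characteristics), Table 7 (therapies in Lines 1 to 3, with mean duration by class) and a bar chart.

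**The concern.** The subgroup is labelled and justified by era, but the analysis set admits patients by something that happens after the era has closed. A woman who started therapy in early 2016 and died before receiving a CDK4/6 inhibitor is absent. So is one who stayed on her 2016 therapy unchanged to the end of the study period. Those who remain survived, stayed in care at the site and had the drug added or given in a later line.

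The 2019 column is conditioned on receipt too, but not in the same way, because a 2019 starter can receive the drug in her first line. A reader who compares the columns would take the difference as a change in practice, when part of it may come from who was allowed into each column. Nothing in the table titles or footnotes warns of this.

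**Working it through.** There is no planned figure to reproduce: Protocol 9.5 says that sample size calculations do not apply. The check is one of logic, with dates and counts as context.

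**Step 1. Trace the set.** Criterion 4 (SAP 4.1) defines the full analysis set. SAP 4.3 assigns that set to the secondary objective. SAP 4.4 and 7.2 take the two subgroups from it, and these fill Tables 4 and 7. No visible passage defines a wider set, so receipt of a CDK4/6 inhibitor is 100% in both columns by construction.

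**Step 2. How a 2016 starter can qualify.** The SAP places introduction after May 2016. Protocol 9.9 says that palbociclib use before approval is not represented, and receipt within a clinical trial is an exclusion. What remains is later receipt, up to 1 October 2021.

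**Step 3. Compare the conditions on the two columns** (introduction taken as 1 June 2016, following the SAP's dating):

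| | 2016 starters | 2019 starters |
|---|---|---|
| Wait until the drug is available | 1 day (start 31 May) to 152 days (start 1 January) | none |
| Days to receive it, up to 1 October 2021 | 1948 (from 1 June 2016) | 1004 (from 1 January) to 854 (from 31 May) |
| Can start the drug with Line 1 | no | yes |

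The ratio of time available is 1948/1004 = 1.94 to 1948/854 = 2.28.

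**Step 4. Effect on Table 7.** Every Line 1 duration in the 2016 column belongs to a patient who went on to receive the drug. A 2019 patient who starts it in Line 1 carries no such condition.

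**Step 5. Can the distortion be sized?** No. It depends on the chance of later receipt after each first therapy, which the documents do not give. As an illustration with assumed values only, let 30% of 2016 patients start chemotherapy, with chances qC of later receipt after chemotherapy and qE after endocrine therapy. The chemotherapy share among those retained is 0.3qC / (0.3qC + 0.7qE):

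- qC = 0.2, qE = 0.4: 0.06 / (0.06 + 0.28) = 17.6%
- qC = 0.1, qE = 0.6: 0.03 / (0.03 + 0.42) = 6.7%
- qC = qE: 30%, no distortion
- qC = 0.4, qE = 0.2: 0.12 / (0.12 + 0.14) = 46.2%

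Neither size nor direction is fixed.

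**Step 6. Numbers per window, as context.** Diagnosis runs from 1 January 2016 to 1 July 2021, 66 months, and each window is 5 months. The amendment logs put the sample below 30% of 180, so at most 53. Assuming even accrual and that this total is the treated cohort:

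- 53 × 5/66 = 4.0
- 180 × 5/66 = 13.6
- 27 × 5/66 = 2.0 (27 is an assumed low case, 15% of 180)

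These apply a diagnosis rate to therapy starts, and 180 counts diagnoses rather than treated patients. They show how thin the columns are; they do not measure the selection.

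**Step 7. Test entry.** The SAP 7.2 row for this table still lists comparison tests (t-test, ANOVA and others). Protocol 9.7 and SAP 3.1 rule out inference, and the matching row in SAP 7.2.2 lists only descriptive statistics and bar charts.

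**The case against.** **The intended population is not settled.** SAP 4.4 and 7.2 speak of ABC/MBC patients without a receipt condition, and Protocol 9.5 describes inclusion without it. Perhaps a wider group was meant. This stands in part. A study-size paragraph does not override numbered criteria that the abstract and Protocol 9.2 repeat, but relabelling should not be imposed before the sponsor has said which population applies.

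**The plan already carries caveats.** Protocol 9.9 warns of selection and channeling bias. SAP 4.4 makes subgroups depend on adequate sample size, and SAP 7.2 calls the windows "contingent upon clinician input and review of primary objective results and are subject to change". The study title also limits the study openly to recipients. All true, but none names this conditioning, and moving the dates would not lift criterion 4.

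**It is a small descriptive subgroup.** Also true, and it limits the severity. A descriptive table must still describe the population on its label.

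**Stronger readings that the documents do not support:**

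- A reader might infer that earlier therapy is tabulated nowhere. In fact Tables 6, 7 and 12 list lines that can precede the first CDK4/6 inhibitor; none isolates them.
- A reader might infer that the plan means to report uptake and cannot. SAP 7.2 mentions uptake only to explain the choice of 2019, and no table shell reports a proportion taking up the drug.
- A reader might take the small window counts as the size of the bias. They are not.

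**Conclusion.** The point holds and should be fixed. On the visible text, the 2016 column is a group selected on later receipt and reported as pre-CDK practice. The 2019 column is selected on receipt under different conditions. Tables 4 and 7 and the related bar chart can describe early therapy among eventual recipients; they cannot represent general practice before introduction, and differences between columns mix era with selection.

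The conclusion rests on the numbered criteria standing as written and on the SAP's own date for introduction. Figure 1 and some redacted text, including a block directly after the subgroup definitions, cannot be seen. It would be too strong to say that the comparison is biased in a known direction or by a known amount.

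Table 8, on therapies after the CDK4/6 inhibitor, is unaffected. So is the primary objective, which concerns palbociclib recipients by design.

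**What to change.** 1. **Settle the population.** Reconcile SAP 4.4, SAP 7.2 and Protocol 9.5 with criterion 4 by stating which patients the pre/post-CDK analysis uses.
   - *If the numbered criteria stand:* in SAP 4.4, 7.2 and Tables 4 and 7, rename both groups as eventual CDK4/6 inhibitor recipients by era of starting systemic therapy. State that they do not represent general pre-introduction practice and that 2016 Line 1 durations are conditioned on later receipt. This is mainly SAP wording, plus one line in Protocol 9.5.
   - *If a true era comparison is intended:* define a separate analysis set without criterion 4, for both windows, by protocol amendment. This needs ethics approval (Protocol 10.3) and further extraction, with data collection planned to end on 31 March 2023.
2. **Delete the comparison tests** from the SAP 7.2 row for this table. No cost.
3. **Optional:** add one table that isolates ABC/MBC lines before the first CDK4/6 inhibitor in the full analysis set, to pair with Table 8. The therapy dates and lines are already among the planned variables (Protocol Table 1).

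If the criteria stand, the price is a narrower stated conclusion and, if item 3 is taken, one extra table.
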